### **1.3.6 Good Clinical Practice Breach**

All serious good clinical practice (GCP) breaches will be reported in the clinical study report (CSR).

If a GCP breach prevents the sponsor from verifying the validity of the data from a particular site, then the resulting data from that site will not be used in the data analyses described in Section 4.

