**Table 4 Participant Analysis Sets**

Participant Analysis Set	Description
Full analysis set	All randomized participants: participants will be included in the analyses according to the treatment they were assigned.
Immunogenicity analysis set	All participants with at least one ADA assessment; participants will be grouped according to treatment received.
Pharmacokinetic analysis set	All participants who have measurable concentrations of ocrelizumab unless major protocol deviations or unavailability of information (e.g., exact blood sampling time) occurred or if data are unavailable, not plausible, or incomplete which may interfere with PK evaluation. Excluded cases will be documented together with the reason for exclusion.
Safety analysis set	All participants who received at least one infusion (partial or complete) of study drug; participants will be included in the analyses according to the treatment they received.

ADA = anti-drug antibody; PK = pharmacokinetic.

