#### **4.2.2 Main Analytical Approach for Primary Estimand**

The primary estimand is the difference in time to onset of cCDP12, as expressed by the HR, between the higher and approved dose of ocrelizumab arms in patients with RMS and regardless of adherence to the randomized treatment or use of an approved MS disease-modifying therapy (DMT) medication. More specifically, the estimand has the following attributes:

**Population:** Patients with RMS.

**Endpoint:** Time to onset of cCDP12.

**Summary Measure and Primary Estimator:** The HR will be used to quantify the difference in time to onset of cCDP12 between study treatments, and will be estimated from a Cox proportional hazards regression model, stratified by the randomization stratification factors. The statistical significance of the estimated HR will be calculated by using the log-rank test, stratified by the randomization stratification factors.

In order to estimate the primary estimand, the following **intercurrent event** handling strategies will be applied:

**Early discontinuation from study treatment:** All data pre and post treatment discontinuation will be included in the analysis following the treatment-policy strategy.

**Initiation of an approved MS DMT medication:** All data pre and post initiation of alternative MS treatment will be included in the analysis following the treatment-policy strategy.

**Pregnancy:** All data pre and post pregnancy onset will be included in the analysis following the treatment-policy strategy.

**Death:** This is anticipated to be very rare, but in case of occurrence, it will be handled as a progression event in line with the composite strategy.

Every effort will be made to collect the data post early discontinuation from study treatment or initiation of an approved MS DMT medication until primary analysis.

Intermediate missing assessments at scheduled visits prior to the last EDSS, 9-HPT, or T25FWT assessments will not be imputed. For patients with initial disability progression based on EDSS or  $\geq 20\%$  increase in T25FWT or 9-HPT, data collected at the next scheduled visit or treatment discontinuation visit will be used to confirm disability progression.

Missing data resulting from patients that withdraw their consent to participate in the study and/or a serious GCP breach will not be imputed.

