#### **4.5 SAFETY ANALYSES**

The safety analysis set (SAS) is described in Section 3. All safety parameters will be summarized and presented in tables on the basis of this analysis set. Randomized patients who receive incorrect therapy will be summarized in the group according to the rules laid out in Section 3. Patients who received at least one dose of ocrelizumab above 600 mg will be grouped in the higher dose of ocrelizumab arm.

Patients who are not randomized but who receive study drug will be included in the SAS and summarized according to the therapy actually received.

All patients who received at least one infusion (partial or complete) of study drug with patients grouped according to actual treatment received will be included in the analysis.

- The safety data will be summarized regardless of premature study treatment discontinuation or switch to an approved MS DMT medication (including commercial ocrelizumab).
- Additionally, the safety data may also be summarized regardless of premature study treatment discontinuation but until switching to an approved MS DMT medication (including commercial ocrelizumab).

Safety will be assessed through summaries of exposure to study treatment, AEs, changes in laboratory test results, and changes in vital signs. All verbatim AE terms will be mapped to MedDRA thesaurus terms, and AE severity will be graded according to National Cancer Institute Common Terminology Criteria for Adverse Events (NCI CTCAE) v5.0. All AEs, SAEs, AEs leading to death, AEs of special interest, and AEs leading to study treatment discontinuation that occur on or after the first dose of study treatment (i.e., treatment-emergent AEs) will be summarized by mapped term,

appropriate thesaurus level, and severity grade. For events of varying severity, the highest grade will be used in the summaries. Deaths and cause of death will be summarized. Relevant laboratory and vital sign (pulse rate, and blood pressure) data will be displayed by time, with grades identified where appropriate. Additionally, a shift table of selected laboratory tests will be used to summarize the baseline and maximum post baseline severity grade. Changes in vital signs will be summarized.

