The number of patients who experienced a related AE will be summarized by SOC and PT. AEs will be summarized by SOC and PT by intensity grade. Multiple occurrences of the same event within a patient will be counted once at the greatest intensity/highest grade for this PT. For AEs leading to death, the most extreme intensity will be overwritten by Grade 5 (death). Any AEs and the SOC overall rows of the summary table will count patients according to AEs by intensity (grade).

All patient deaths, regardless of treatment received, will be listed.

SAEs will be defined as all SAEs including serious MS relapses and serious IRRs. The number of patients who experienced an SAE will be summarized by SOC and PT.

Related SAEs will be summarized by SOC and PT. Additionally, the most frequent SAEs ( $\geq 1\%$ ) will be presented by SOC and PT.

A patient may experience an AE that leads to the discontinuation of his/her study treatment. Discontinuation of study treatment for an AE may not necessarily lead to discontinuation from the study because the patient can remain in the DBT phase without treatment. Only AEs that led to the discontinuation of study treatment are of interest. Patients who withdraw early from the study because of AEs will be summarized under disposition. The number of patients who experienced an AE that led to discontinuation of study treatment will be summarized by SOC and PT. The number of patients who experienced an AE that led to modification or interruption of study drug will be summarized by SOC and PT.

For each treatment group, the incidence count for each AE PT will be defined as the number of patients reporting at least one treatment-emergent occurrence of the event. The incidence rate will be calculated as the incidence count divided by the total number of patients in the population. Each table will also present the overall number of patients experiencing at least one AE and the total number of AEs reported (multiple occurrences of the same AE in 1 patient will be counted only once).

The rate per 100 patient-years by treatment group (along with the 95% CI) will be calculated for specific events of interest such as all AEs, SAEs, infections and serious infections (see Section 4.5.4), opportunistic infections (OIs; see Section 4.5.5), and malignancies (see Section 4.5.6).

- The number of AEs per 100 patient-years is calculated as:

$(\text{Total number of AEs} \div \text{Total number of patient-years}) \times 100$

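### As written, the site-exclusion rule for GCP breaches in SAP 1.3.6 also takes a site's deaths and serious adverse events out of the safety outputs

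*SAP*

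**What the plan says.** SAP 1.3.6 has two parts. Serious GCP breaches are to be reported in the study report. It then sets an exclusion with this trigger: "If a GCP breach prevents the sponsor from verifying the validity of the data from a particular site". The consequence is mandatory: "then the resulting data from that site will not be used in the data analyses described in Section 4".

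Section 4 of the SAP contains efficacy (4.2 to 4.4), safety (4.5) and other analyses (4.6). Within it:

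- Section 4.5, on the safety analysis set: "All safety parameters will be summarized and presented in tables on the basis of this analysis set".
- Section 4.5.2, on SAEs: "The number of patients who experienced an SAE will be summarized by SOC and PT".
- Section 4.5.2, on deaths: "All patient deaths, regardless of treatment received, will be listed".
- Section 4.2.2, on efficacy data lost this way: "Missing data resulting from patients that withdraw their consent to participate in the study and/or a serious GCP breach will not be imputed".

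Table 4 defines the safety analysis set as "All participants who received at least one infusion (partial or complete) of study drug" and the full analysis set as "All randomized participants: participants will be included in the analyses according to the treatment they were assigned". Neither definition has a site exception. Protocol 6.5 also bases safety on everyone who received at least one infusion.

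**The concern.** Setting aside unverifiable efficacy data is defensible, because a confirmatory estimate should not rest on measurements that nobody can check. Safety is different. A death or SAE at such a site is still a report about a treated patient, and the usual course is to show it with a caution. The rule draws no such distinction and applies one instruction to the whole of Section 4.

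This trial compares a higher dose with the approved dose, and describing the safety of the higher dose is one of its stated objectives. A reader of the report would expect the safety tables to cover every treated patient, because Table 4 and the protocol say so. If the rule had been applied, they would not. SAP 4.7, which lists departures from the protocol's planned analyses, names only pregnancy as an added intercurrent event.

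**Working it through.** **Reading the passages together.** Take a treated patient at a site where the 1.3.6 trigger is met, and suppose the patient dies.

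1. Table 4 and protocol 6.5 place the patient in the safety set.
2. Section 4.5 has deaths summarized, and 4.5.2 has all of them listed.
3. Both outputs are described in Section 4, so 1.3.6 says the site's data are not used for them.
4. No sentence says which instruction prevails.

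The same steps apply to SAEs, adverse events of special interest and events leading to treatment discontinuation, all of which 4.5 summarizes.

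The effect on denominators is also open. Section 4.5.2 divides patients with an event by all patients in the population. If the site's patients are removed, numerator and denominator both fall. If they stay in the safety set while their data are unused, they count in the denominator and cannot count in the numerator, so incidence is understated.

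**Size for safety.** Inputs are 865 randomized (SAP 2.2), about 220 sites (protocol 9.5) and 2:1 allocation.

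- Patients per average site: 865/220 = 3.9, or 1/220 = 0.45% of the trial. The 220 was planned for 786 patients, and the actual number of sites is not given.
- Higher-dose arm, if the ratio held exactly and all were treated: 865 × 2/3 ≈ 577.
- An event seen once in that arm: 1/577 = 0.17%. If it occurred at the excluded site, the table shows none.

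**Size for the primary result.** The plan's own figure reproduces. Events = (1.960 + 0.842)² / [(2/3)(1/3)(ln 0.66)²] = 7.85 / (0.2222 × 0.1727) = 204.6, so 205, with 80.1% power. One average site carries 205/220 = 0.93 events. Losing it leaves 204.1 events and 79.9% power.

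For the p-value, the log-rank variance is V = 205 × 2/9 = 45.6, with square root 6.75. Removing one higher-dose event adds 1/3 to the score in favour of the higher dose, and removing one control event subtracts 2/3. Starting from z = 1.75 (p = 0.080):

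| Removed | Calculation | z | p |
|---|---|---|---|
| 1 higher-dose event | (11.81 + 0.33)/√(204 × 2/9) | 1.80 | 0.071 |
| 1 control event | (11.81 − 0.67)/√(204 × 2/9) | 1.65 | 0.098 |
| 5 higher-dose events | (11.81 + 1.67)/√(200 × 2/9) | 2.02 | 0.043 |
| 3 control events | (11.81 − 2.00)/√(202 × 2/9) | 1.46 | 0.14 |

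Five events at the overall rate of 205/865 = 23.7% imply a site of about 5/0.237 = 21 patients, over five times the average.

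A leave-one-site-out simulation gives the same picture. It assumed 865 patients, 220 sites, a true hazard ratio of 0.75, about 201 events and an unstratified test. Removing one site moves p by a median of about 0.005. Removal crosses 0.05 for about 26% of sites when p is already between 0.04 and 0.06, and for about 3% to 6% when p is 0.03 to 0.04 or 0.06 to 0.07. The planned test is stratified, so these figures are approximate.

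**The case against.** The best defence has four parts.

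*Table 4 says who belongs to a set, and 1.3.6 says which data are usable. A specific rule qualifying a general one is not a contradiction.* This is fair as to form, and it is why a cross-reference is part of the remedy. It does not rescue the outcome: a patient who stays in the set with no usable events gives an incidence that is too low.

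*The wording could cover only data affected by the breach, a listing is arguably not an analysis, and the deaths sentence concerns treatment received, not site validity.* These readings narrow what is lost. None exempts the safety summaries.

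*Safety oversight does not depend on these tables.* This stands. Immediate and expedited reporting (protocol 5.4 and 5.7) and iDMC monitoring (SAP 1.3.5) continue, and serious breaches appear in the study report. A reader might infer that such events would disappear from safety surveillance. The documents do not support that. The loss is confined to the report's safety outputs.

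*The timing of the decision is already controlled.* This largely stands. A reader might infer that a site could be dropped after the results are seen in order to move the primary p-value. The plan does not point that way. The trigger is verifiability, not outcome, and the rule is mandatory once triggered. The sponsor is blinded apart from staff whose roles require allocation (SAP 1.3.2). Cleaning and database lock precede unblinding (SAP 2.3), and deviations are reviewed for serious breach (protocol 9.2). What is missing is a sentence tying the exclusion decision to that sequence.

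**Conclusion.** The safety part holds. This is a stated rule that, if followed, gives a worse result than the plan's own safety definitions intend. It is conditional, since the documents report no breach. It is also usually small, about 0.45% of patients for an average site, and it matters most for rare serious events, where one case may be all there is.

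The effect on the primary result is not a reason to change the plan. Power moves from 80.1% to 79.9% for an average site. A change in significance needs a result already very close to 0.05, or an unusually large and one-sided site. The missing statement on timing is a clarification that supports the main point.

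These sizes assume 220 sites, exact 2:1 allocation and an unstratified approximation. The reading of the text does not depend on them.

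**What to change.** Reword SAP 1.3.6 in three respects:

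1. Limit the exclusion to the efficacy analyses.
2. Keep the site's deaths, SAEs, adverse events of special interest and adverse events leading to discontinuation in the safety outputs, or show them by arm in a separate flagged table. Add a cross-reference in Table 4 so that the safety set and the exclusion rule read together.
3. State that any site exclusion is decided and documented before sponsor unblinding.

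Repeating the primary analysis with the site restored is optional. It uses data the sponsor could not verify, and would inform mainly when the result is very close to 0.05.

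The cost is a few sentences now, and one extra table at most if a breach occurs. The downside is that some unverified safety reports are displayed, and the flag tells the reader so.

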## **2. STATISTICAL HYPOTHESES AND SAMPLE SIZE DETERMINATION**

### **2.1 STATISTICAL HYPOTHESES**

The hypotheses to be tested for the primary estimand are:

- H0 (null hypothesis): There is no difference in the time to onset of cCDP12 between the higher and approved dose of ocrelizumab arms.
- H1 (alternative hypothesis): There is a difference in the time to onset of cCDP12 between the higher and approved dose of ocrelizumab arms.

This will be tested at the 5% significance level ( $\alpha = 0.05$ ) against two-sided alternatives.

Null and alternative hypothesis of similar form will be tested for all secondary efficacy endpoints, i.e., there is no difference (null hypothesis) vs there is a difference (alternative hypothesis) in endpoint between the higher and approved dose of ocrelizumab arms, except for NfL endpoints within each study arm where the hypotheses to be tested are:

- H0 (null hypothesis): There is no change in NfL from baseline at Week 48 within the higher or approved dose of ocrelizumab arms.

- H1 (alternative hypothesis): There is a change in NfL from baseline at Week 48 within the higher or approved dose of ocrelizumab arms.

The secondary efficacy estimands will be tested in the hierarchical order listed below, if the primary estimand and each preceding estimand have reached the significance level of 0.05:

- Time to onset of 24-week composite confirmed disability progression (cCDP24)
- Time to onset of 12-week confirmed increase in T25FWT (CIT25FWT12)
- Time to onset of cCDP12 independent of protocol-defined relapses (cPIRA12)
- Change from baseline in NfL at Week 48 for patients assigned to OCR HD arm
- Change in NfL from baseline at Week 48 for patients assigned to OCR approved dose arm
- Time to onset of 12-week confirmed disability progression (CDP12)
- Time to onset of 48-week composite confirmed disability progression (cCDP48)
- Time to onset of 12-week confirmed  $\geq 4$ -point worsening in Symbol Digit Modalities Test (CWSDMT12)
- Time to onset of 24-week confirmed  $\geq 8$ -point increase in 12-Item Multiple Sclerosis Walking Scale (CIMSWS24)
- Annual rate of percent change from baseline in total brain volume

The full description of the estimand attributes for the secondary estimands is provided in [Table 1](#).

## 2.2 SAMPLE SIZE DETERMINATION

The sample size was determined based on data from Studies WA21092 and WA21093 (Opera I and Opera II, respectively) and Kappos et al. (2018). A two-group test of equal exponential survival curves was used to determine the sample size for the time to onset of cCDP12. With a 2:1 randomization ratio between the higher and approved dose treatment arm and assuming recruitment of 390 patients per year, 5% annual dropout rate, a control group progression rate of 21.5% and 5% two-sided Type I error, it is predicted that a sample size of approximately 786 (524:262) patients will be required to achieve 80% power to detect a HR of 0.66 based on 205 cCDP12 events. Therefore, the DBT phase will run until at least 205 cCDP12 events are observed.

Between November 2020 and December 2021, a much faster recruitment rate was observed than anticipated and 798 patients were randomized. Of the 798 randomized patients, 116 and 135 patients were participating at sites in Ukraine and Russia, respectively. To mitigate a potential withdrawal of patients or loss of data from Ukraine and Russia, due to the current conflict in the Ukraine, starting in February 2022, 67 additional patients were randomized from April 2022 to August 2022 resulting in a total sample size of 865 patients (10% more than the planned sample size in the absence of the war) for this study.

Supplementary analyses have been proposed in Section 4.2.4 to investigate the impact of the Russia-Ukraine war on the primary analysis. Furthermore, analyses to assess the impact of the war on study conduct have been proposed in Section 4.6.3.

### **2.3 ANALYSIS TIMING**

The clinical cutoff date (CCOD) will be approximately when the last enrolled patient completes at least 120 weeks of study treatment, provided that the total number of cCDP12 events for the primary efficacy analysis is approximately 205. As of the present time, 205 cCDP events have been observed. Therefore, the CCOD will take place when the last enrolled patient completes at least 120 weeks of study treatment, which is currently scheduled to be in December 2024.

Unblinding of the Sponsor will occur several weeks following the CCOD when all data up to the CCOD are cleaned and the database is locked for the primary analysis (called the primary database lock in the remainder of the document). The primary analysis will include all data up to the CCOD for both safety and efficacy endpoints, unless stated otherwise.

The primary and secondary efficacy endpoints that are not planned to be analyzed with respect to a specific time point will use all available data in the database at the time of primary database lock. The other endpoints that are planned to be analyzed with respect to a specific time point (e.g., change from baseline to Week 48 or 120) will use data collected for each patient only up to and including the pre-specified time point. Any data collected for patients beyond that time point will not be included in the endpoint derivation or analysis.

At the end of the study an additional analysis comprising all data collected including the OLE will be performed. These analyses will be documented in a separate SAP.

### **3. ANALYSIS SETS**

All efficacy endpoints will be analyzed using the full analysis set (FAS), which is described in Table 4. Table 4 also covers analysis sets relevant to the PK, immunogenicity, biomarker and safety objectives of this study.

**Table 4 Participant Analysis Sets**

Participant Analysis Set	Description
Full analysis set	All randomized participants: participants will be included in the analyses according to the treatment they were assigned.
Immunogenicity analysis set	All participants with at least one ADA assessment; participants will be grouped according to treatment received.
Pharmacokinetic analysis set	All participants who have measurable concentrations of ocrelizumab unless major protocol deviations or unavailability of information (e.g., exact blood sampling time) occurred or if data are unavailable, not plausible, or incomplete which may interfere with PK evaluation. Excluded cases will be documented together with the reason for exclusion.
Safety analysis set	All participants who received at least one infusion (partial or complete) of study drug; participants will be included in the analyses according to the treatment they received.

ADA = anti-drug antibody; PK = pharmacokinetic.

## **4. STATISTICAL ANALYSES**

### **4.1 GENERAL CONSIDERATIONS**

All statistical hypotheses for the primary and secondary endpoints and treatment comparisons will be tested at the 5% significance level ( $\alpha=0.05$ ) against two-sided alternatives.

All primary and secondary efficacy endpoints will be stratified by region, age at screening, baseline EDSS and baseline body weight for analysis. The regional stratifications are United States and ROW. The age categories are  $\leq 45$  years and  $> 45$  years. The EDSS categories are  $< 4.0$  and  $\geq 4.0$ . The body weight categories are  $< 75$  kg and  $\geq 75$  kg.

The baseline for the primary endpoint is the date of randomization. The baseline value of the endpoint, e.g., EDSS, T25FWT and 9-HPT values, is the most recent value up to and including the date of randomization but before first infusion of study drug. A subject with delayed dosing may receive the first dose 2 weeks after the baseline visit; if an EDSS, T25FW or 9-HPT score is recorded between the randomization date and the date of the first dose, this value will be considered as a post-baseline assessment.

FAS will be used in the analysis of the primary and secondary estimands, and exploratory efficacy endpoints. Safety analysis set (SAS) will be used to summarize safety data. For analysis purposes, the time of treatment discontinuation will be defined as 24 weeks after the last dose prior to the date of treatment discontinuation recorded in the electronic Case Report Form (eCRF).

